### Ophthalmologic:

The most important adverse effect of hydroxychloroquine is retinal toxicity. In a retrospective case-control study of 2,361 individuals who had taken hydroxychloroquine for at least 5 years, retinopathy was seen in 7.5% of users when assessed with spectral domain optical coherence tomography and 10 degree standard automated perimetry visual fields; as duration of use increases, an unknown, but

higher percentage that varies with the daily dose was seen. The risk of retinopathy was duration- and dose-dependent, and was less than 2% within 10 years in those taking 4-5 mg/kg/day. There is negligible risk when duration of therapy <6 months and it is unlikely to occur if dose is <5 mg/kg/day actual body weight (generally equivalent to 6.5 mg/kg/day ideal body weight) up to 400 mg/day. Moreover, retinopathy detected by these sensitive techniques is not equivalent to clinically apparent or significant visual effects. Despite longstanding use of hydroxychloroquine for malaria therapy in very young children, there is a dearth of information about retinopathy, suggesting its rarity. Current practice recommendation by the American Academy of Ophthalmology is annual examination after 5 years of drug exposure in those on daily doses  $\leq 5.0$  mg/kg with no major risk factors.

Dermatologic AEs (pruritus, allergic rashes, and increased skin pigmentation), neuromuscular AEs (muscle aches), and insomnia each occur 1% of the time and resolve within 1-2 weeks with continued therapy.

Cardiovascular: Hydroxychloroquine has the potential to cause QT prolongation and should not be administered with other drugs that have a potential effect on the QT interval (*see Drugs Interactions; section 7.2.4.2*). In addition, rare cases of cardiomyopathy have been reported in those over age 50 who received high doses of hydroxychloroquine over a long duration.

Thrombocytopenia and hemolysis are rare and are probably associated with high doses, other drugs, or G6PD deficiency.

There are case reports of allergic reactions (urticarial, angioedema), abnormal liver function tests, and skeletal muscle myopathy, which are reversible over time.

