 6= May include samples for pharmacokinetic assessment, RNA, plasma, serum, DNA, measures of B and T cell number and function to understand the effect of therapy on the immune system and infectious disease. The schedule for these assessments may vary as appropriate. At no time will the blood draw volume exceed what is allowable according to the participant’s age and body weight (For participants <18 years, 5 mL/kg per visit, 9.5 mL/kg in an 8 week period). Responses to clinically indicated immunizations may be determined through analysis of pre- and post-dose samples.  
 7= Ophthalmology examination: baseline examination may occur any time from screening until three months after randomization. Subsequent examinations will occur annually for all participants, starting at the 12 month visit.  
 8 = All subjects may have interim contact with study personnel for formal inquiry about adverse events and presence or absence of diabetes related symptoms. This interim contact does not require an in-person visit.

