A total of 201 participants will be randomized in a 2:1 allocation to treatment with hydroxychloroquine (n=135) vs. placebo (n=66). Randomization will be conducted using block randomization with variable block sizes with stratification on (1) whether or not participants have been previously treated for T1D prevention, and (2) age group (< 8 years old vs. 8 years old or older).

The assumptions underlying the estimated sample size for this design are: (1) 40% two-year event rate in the placebo group, (2) detectable hazard ratio of 0.50 (i.e. 22.5% two-year event rate) in the hydroxychloroquine group, (3) less than a 10% two-year dropout rate in both groups, and (4) survival curves which are consistent with exponential survival distributions. Even testing for variable proportions of each stratum and with slight variation in the expected hazard rates for the placebo group across the strata, our proposed sample size of 201 participants will provide at least 83% power to detect a hazard ratio of 0.50 in the time to T1D stage progression between the two treatment groups using a stratified Cox regression model⁷⁵.

Under the above assumptions, the target total number of events is equal to 80; i.e., the final analysis will be conducted once 80 events (confirmed abnormal glucose tolerance, diabetes) have been observed. If the accrual rate is 50 patients per year, with the above assumptions it is estimated that the enrollment period will last approximately 4 years with a total study duration of approximately 6 years (4 years of accrual + minimum of 2 years of follow-up) to provide a sufficient number of events to detect the assumed difference.

The final test of significance up to the six-year time point will employ group sequential critical values to protect against inflation in the type I error probability due to interim assessments of the emerging data for review by the DSMB (see Section 8.5).

Note the accrual period and the study sample are only projections, since the actual accrual rate and the loss-to-follow-up rate are unknown. As the study progresses, more accurate projections of the study end date will be computed based on the observed rate of enrollment, the observed number of events, and the observed rate of loss-to-follow-up. These data will be provided to the DSMB and the TrialNet governing body, and if need be, this document will be amended.

6. Interim Monitoring Plan

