All subjects who received any study treatment (including control) but excluding subjects who drop out prior to receiving any treatment.

2. Timing of Analyses

The final analysis will come after the total number of events (confirmed abnormal glucose tolerance) in the placebo group is between 64 and 70. This will result in detectable hazard ratios of 0.496 to 0.512 to achieve the planned 80% statistical power when testing at the 0.05 level (2-sided) for the primary analysis.

3. Missing Data

In general, missing values will be assumed to be *missing completely at random (MCAR)* unless empirical evidence to the contrary can be established internal to the study. The methodology employed in analyzing time-to-T1D utilizes whatever follow-up has been recorded for each subject (i.e., maximum utilization of follow-up time). Presuming no evidence against MCAR no methods will be employed to impute additional follow-up of subjects that drop out (i.e., lost to follow-up). All secondary endpoints will use the complete-case analysis approach which limits the analytical cohort to those subjects that have the secondary endpoint of interest measured and recorded. In modeling to adjust for risk factors associated with the endpoint (i.e. covariates), missing values will be assigned the mean from the known covariate cohort. This simple rule will be employed only if the percent missing is less than 10% for the analytical cohort. If the missing is 10% to 20% a separate indicator for missing will be included in the modeling. If the missing in exceeds 20% the covariate will be removed from consideration.

8. Safety Analyses

Safety will be evaluated with summary of adverse events for the safety population. The following parameters will be assessed during the study:

Adverse Events

The summary statistics will be produced in accordance with Section 8. Treatment emergent adverse events (AEs) are those events that occur after the baseline assessment. Only Grade 2 or greater adverse events were reported in this study. The incidence of the following AEs will be reported:

A tabular summary of AE will present: Number of subjects with any AE; Number of SAEs with outcome death; Number subjects with SAE; Number subjects with AEs leading to discontinuation of study drug, even if by protocol; Number of subjects with AEs leading to discontinuation of study; Total number of AEs; Total number of SAEs [TABLE].

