The Adverse Events summary tables will include number of adverse events, the number of subjects in each treatment group in whom the event occurred, and the incidence of occurrence and should be grouped by system organ class, preferred terms and/or other interested variables (e.g., relatedness, intensity and seriousness). [TABLE]

When calculating the incidence of adverse events, or any sub-classification thereof by treatment, time period, severity, etc., each subject will only be counted once and any repetitions of adverse events will be ignored; the denominator will be the total population size. Deaths, Serious Adverse Events and other Significant Adverse Events

All formal testing of adverse effects will be based on the subject as the experimental unit. Thus, for comparing incidence of AE within system organ by treatment group, a one-sided Fisher's exact test will be conducted at 0.05 level (higher incidence in experimentally treated group is the alternative hypothesis). Also, highest AE grade will be determined for each subject and compared by treatment group using a 2 sample Wilcoxon test (one-sided at 0.05). No correction for multiple testing will be employed in order that the statistical power is maintained.

9. Reporting Conventions

P-values ≥ 0.01 will be reported to 2 decimal places; p-values less than 0.01 and >0.001 will be reported to 3 decimal places; p-values less than 0.001 will be reported as " <0.001 ". The mean, standard deviation, and any other statistics other than quantiles, will be reported to one decimal place greater than the original data. Quantiles, such as median, or minimum and maximum will use the same number of decimal places as the original data. Estimated parameters, not on the same scale as raw observations (e.g. regression coefficients) will be reported to 3 significant figures.

10. Per Protocol Analysis

Quantifying the evidence of any dose response relationship is part of a complete analysis of any well-run and completed clinical trial. This is especially true when the trial is negative when testing the primary outcome. To explore whether there is evidence that protocol treatment deviations may have played a role in the negative outcome, we plan to assess the treatment hazard ratio by the degree of compliance (percent missed infusions) to the protocol scheduled dose in a quantitative manner.

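### The rule in SAP 8 divides adverse-event incidence by the total population even when split by time period, so any by-period table made under it would understate later periods

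*SAP*

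**What the plan says.** SAP 8, under Adverse Events, lays down the counting rule for incidence: "When calculating the incidence of adverse events, or any sub-classification thereof by treatment, time period, severity, etc., each subject will only be counted once". The same sentence goes on: "any repetitions of adverse events will be ignored; the denominator will be the total population size". The safety population in SAP 7 is "All subjects who received any study treatment (including control) but excluding subjects who drop out prior to receiving any treatment", so it is not limited to people still followed in a given period. Neither document plans person-time rates, a number-at-risk denominator or time to first AE for safety.

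SAP 5 and protocol 8.4 plan about four years of accrual and at least two years of follow-up, so potential follow-up runs from two to six years. Protocol 7.3 withdraws participants from therapy once they reach abnormal glucose tolerance. Protocol 3.9.2 and 8.1 let them stay, off drug, for monitoring and safety assessments if they choose.

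In Appendix 2 the Adverse Events row is marked at baseline, months 1, 3 and 6, and every six months after that. It is blank in the month 9 column. Footnote 8 says of the interim contact: "All subjects may have interim contact with study personnel for formal inquiry about adverse events". Footnote 2 says AE assessment is part of all visits.

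**The concern.** With a fixed denominator, anyone not under observation in a period is treated as observed and free of events. The later the period, the more such people there are, so a constant AE rate prints as a declining one and a rising rate is damped. Protocol 7.2 says of the toxicity that it calls most important: "The risk of retinopathy was duration- and dose-dependent". The late periods are therefore the ones a reader of a by-period table would most want to trust. The distortion lies across periods within an arm, so using the arm's own N does not remove it. If the drug works, the arms also lose observation at different speeds, and the same rule then distorts the late between-arm comparison.

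**Working it through.** **Inputs (SAP 5, matching protocol 8.4).** "A total of 201 participants will be randomized in a 2:1 allocation to treatment with hydroxychloroquine (n=135) vs. placebo (n=66"); "40% two-year event rate in the placebo group"; hazard ratio 0.50; two-year dropout below 10%, taken at the limit; exponential times; four years of accrual, assumed uniform; end at six years.

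**The plan's own figures.** Power with 80 events and 2:1 allocation: √(80 × 2/3 × 1/3) × |ln 0.5| − 1.960 = 2.923 − 1.960 = 0.963, and Φ(0.963) = 83%, as stated. The two-year rate on hydroxychloroquine is 1 − 0.6^0.5 = 22.5%, as stated. The documents give no AE incidence to reproduce.

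**Hazards per year.** Placebo endpoint −ln(0.6)/2 = 0.2554. Hydroxychloroquine endpoint 0.1277. Dropout −ln(0.9)/2 = 0.0527.

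**Share under observation.** At time t after randomization the share is exp(−h·t) × G(t), where G(t) = 1 up to two years and (6 − t)/4 from two to six years. On drug, h = 0.1277 + 0.0527 = 0.1804 (hydroxychloroquine) or 0.2554 + 0.0527 = 0.3081 (placebo). If everyone stays after Stage 2, h = 0.0527. Averaging over each year gives:

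| Share of the year observed | Yr 1 | Yr 2 | Yr 3 | Yr 4 | Yr 5 | Yr 1 ÷ Yr 2 | Yr 1 ÷ Yr 5 |
|---|---|---|---|---|---|---|---|
| Hydroxychloroquine, on drug | 91.5% | 76.4% | 56.1% | 33.5% | 16.8% | 1.20 | 5.4 |
| Placebo, on drug | 86.1% | 63.2% | 41.0% | 21.6% | 9.6% | 1.36 | 9.0 |
| All stay after Stage 2 | 97.4% | 92.4% | 76.8% | 52.1% | 29.7% | 1.05 | 3.3 |

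**What would print.** Assume a constant true rate of 0.20 first AEs per person-year, with each subject counted once per year. The rate is an assumption; the range tried is 0.05 to 0.50. For hydroxychloroquine on drug:

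| Denominator | Yr 1 | Yr 2 | Yr 3 | Yr 4 | Yr 5 |
|---|---|---|---|---|---|
| Fixed, 135 | 16.6% | 13.9% | 10.2% | 6.1% | 3.1% |
| Number at risk at start of year | 16.6% | 16.6% | 14.7% | 14.0% | 12.7% |
| Person-years to first event in the year | 20 per 100 | 20 | 20 | 20 | 20 |

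With the fixed denominator, year 1 to year 5 runs from 4.5% to 0.8% at a rate of 0.05, and from 36.3% to 6.9% at 0.50, so the fold change hardly depends on the assumed rate. Number at risk at the start of the year removes only part of the fall, because people leave during the year. Dividing first events by all observed person-time is also nearly flat: 16.64/0.915 = 18.2 per 100 in year 1 and 3.10/0.168 = 18.4 in year 5.

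**Two consequences.** To look flat, the true on-drug hydroxychloroquine rate would have to rise about 2.7-fold by year 4 (91.5/33.5) and 5.4-fold by year 5. At the same true rate of 0.20 in both arms, the on-drug year 5 figures would print as 3.1% on hydroxychloroquine and 1.8% on placebo, an excess produced by depletion alone.

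**Inquiry frequency.** The first six months have three AE inquiries (months 1, 3 and 6). Later half-years have one if only the marked AE row counts, or two if the interim contact also counts.

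**The case against.** The best reply is that no by-period table is planned. Time period appears once, in a general counting rule. The tables described in SAP 8 are whole-study summaries, the grouping examples are system organ class, preferred term, relatedness, intensity and seriousness, and the formal tests compare arms, not periods. This stands, and it makes the harm conditional. It does not rescue the rule, which names time period and prescribes the wrong denominator for it.

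A reader might go further in four ways that the documents do not support.

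- That only early, non-progressing participants contribute to later years. Protocol 3.9.2 and 8.1 allow off-drug follow-up after Stage 2, protocol 4.5.1 keeps those who stop for adverse effects on study, and SAP 8 sets no on-drug cut-off for treatment-emergent events. Hence the range from on drug to all followed.
- That rates would fall about 18-fold. That is the on-drug hydroxychloroquine extreme in year 6, when about 5% of a full year is observed.
- That required inquiries fall from three to one. Footnotes 2 and 8 also allow three to two.
- That marking the AE row at month 9 would equalize ascertainment. It would leave two inquiries per half-year against three, and it changes the protocol schedule.

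Retinal findings are sought by ophthalmology examination at baseline and annually, so inquiry frequency does not bear on them; the denominator does. The phrase for the denominator is also loose: taken literally, incidence by treatment would be divided by both arms together. That is one more reason to rewrite the sentence.

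**Conclusion.** The concern holds in a conditional form. If a by-period AE incidence table is produced under the SAP 8 rule, later periods will be understated. With a constant true AE rate, the fall from year 1 to year 5 is about 3.3-fold if all are followed after Stage 2 and about 5.4-fold for hydroxychloroquine on drug. Within the guaranteed two years it is 1.05- to 1.2-fold, so nearly all of the distortion comes after year 2. These sizes rest on the SAP 5 hazards, dropout at its 10% limit, uniform accrual over four years and an end at six years; longer follow-up would raise the late shares. The unequal depletion of the arms further assumes that the drug works as planned. If the true rate rises with exposure, the rule damps or hides the rise and need not show a fall. The rule does not say whether a subject is counted once per period or once overall. Once overall is steeper: 16.6, 11.4, 6.9, 3.4 and 1.4% for years 1 to 5 at a rate of 0.20. Whole-study incidence and the planned between-arm tests are outside this point.

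**What to change.** In SAP 8:

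1. Keep the safety-population N of each arm as denominator for whole-study incidence, and say that it is the arm's N.
2. For any by-period display, define the periods. Report first events per person-time under observation in that period and arm, with a subject counted once per period and person-time ending at the first event in the period. State whether off-drug time after Stage 2 is included.
3. Print the number at risk beside each rate. Do not use it alone as denominator, since it leaves part of the false decline.
4. Base conclusions on between-arm contrasts within a period, not on trends across periods.
5. Note beside the table that AE inquiry is more frequent in the first six months: three, against one or two per half-year later.

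The cost is SAP wording and a different denominator. It needs treatment start, last-contact and event dates, which a time-to-event trial should already hold. No change to the visit schedule in Appendix 2 is needed.

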#### **3.9.2. Follow-up Studies**

Participants who have progressed to Stage 2 T1D (confirmed abnormal glucose tolerance) will have reached the primary study endpoint. These participants who have developed abnormal glucose tolerance but have not progressed to Stage 3 T1D (clinical onset) will have the option to remain in this study without further therapy, undergoing close monitoring and safety assessments until the development of Stage 3 T1D (clinically overt diabetes) or until they enroll in another clinical trial, whichever comes first.

Once participants reach Stage 3 (diagnosis of clinical diabetes), they will no longer be followed in the context of this protocol; however, they will be offered follow-up in the Long Term Investigative Follow-Up in TrialNet (LIFT) Study (TN16). Alternatively, individuals who progress to Stage 3 may be eligible for interventional studies sponsored by TrialNet or other organizations under separate INDs. In the event that a participant wishes to participate in another investigational study whose entry criteria exclude participants who have previously received immunomodulating therapy and is otherwise eligible for the new study, the participant may request and be told of their treatment group assignment for the hydroxychloroquine prevention study. Every attempt will be made to minimize the potential bias that this may introduce. The TNCC will make treatment assignment information available to the site investigator of the new study after the participant is determined to be willing to participate and not otherwise excluded from the new study. Other study group members will not be informed of the treatment assignment information. Mitigation of bias issues must be balanced against safety and interests of participants.

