### **7.3. Protecting Against or Minimizing Potential Treatment Risks**

Participants who have other active serious medical problems will not be enrolled. Frequent monitoring of participants with history, physical examination, and laboratory studies will allow for early identification of adverse events. Every attempt will be made to minimize the number of venipunctures. Participants will be screened for G6PD deficiency and excluded if present.

To mitigate potential ophthalmologic risk, a fundus photograph or examination will be attempted at Baseline, and OCT and visual field examinations will be attempted annually in all participants. Participants with a successful OCT examination may continue with the study per protocol. If neither the OCT nor visual field examination can be successfully completed (e.g., in very young children), these

examinations will be re-attempted on an annual basis while the participant continues on study drug. The target dose of hydroxychloroquine will be 5.0 mg/kg/day to a maximum of 400mg. This is below the dose associated with ophthalmologic risk. Moreover, individuals who reach study endpoint (abnormal glucose tolerance) will be considered to be a non-responder and withdrawn from therapy, thus decreasing duration of exposure.

Individuals will be informed of potential impact on skin, sleep, gastrointestinal symptoms, and muscle aches. If symptoms continue or are intolerable, drug dose may be temporarily reduced or stopped, at the discretion of the investigator in consultation with the medical monitor. If signs or symptoms are consistent with infectious mononucleosis, evaluation may include measurements of EBV serology and viral load as clinically indicated.

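### Crude adverse-event incidence is tested between arms although time under observation can depend on the efficacy outcome; a time-to-first-event comparison should be added

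*SAP*

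**What the plan says.** SAP section 8 (Safety Analyses) sets the counting rule: "each subject will only be counted once and any repetitions of adverse events will be ignored", and "the denominator will be the total population size". For each system organ class "a one-sided Fisher's exact test will be conducted at 0.05 level", with higher incidence on hydroxychloroquine as the alternative. A one-sided Wilcoxon test on each participant's highest grade is added. On multiplicity it says: "No correction for multiple testing will be employed in order that the statistical power is maintained".

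The counting window opens but does not close: "Treatment emergent adverse events (AEs) are those events that occur after the baseline assessment". It is not tied to time on drug.

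On exposure, Protocol 7.3 says that a participant who reaches AGT "will be considered to be a non-responder and withdrawn from therapy". Protocol 3.9.2 says that such participants "will have the option to remain in this study without further therapy". They then have monitoring and safety assessments until Stage 3 or entry to another trial, and Protocol 8.1 repeats this. Footnote 1 of the Schedule of Assessments (Protocol Appendix 2) can be read as ending the six-monthly visits at the study endpoint.

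Protocol 8.3 also plans Fisher tests on severe events and toxicities, without a stated direction. Neither document plans person-years, exposure-adjusted rates or time to first event for safety.

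**The concern.** An ever/never proportion compares arms fairly only if both are watched for about the same time. Here the length of observation can depend on the primary outcome. A participant who reaches AGT leaves treatment and may leave the study; one who does not reach AGT stays on both. If the drug works, its arm is watched for longer and collects more events of every kind, including those unrelated to treatment. The test looks in that same direction, repeatedly across system organ classes and without correction. The maximum-grade comparison has the same dependence.

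The reverse case matters too. If the drug hastened AGT, the hydroxychloroquine arm would be watched for less time and a real excess could be missed, in a trial that enrols children from age 3.

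**Working it through.** **Inputs from the documents.** SAP section 5: 135 versus 66 participants; 40% two-year placebo event rate; hazard ratio (HR) 0.50; two-year dropout below 10% (10% used); 4 years of accrual plus 2 years of minimum follow-up; 80 events; 83% power. Protocol 2.1.2, Figure 4: 68% four-year risk of diabetes from Stage 2.

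**Assumed, because the documents give no figure.** Uniform accrual, so follow-up F is uniform on 2 to 6 years; exponential times; a constant background event rate r of 0.02 to 1.0 per person-year, equal in both arms; 0%, 50% or 100% of progressors staying until Stage 3. The six-monthly OGTT schedule and the confirmation delay are ignored.

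**Plan's own figure.** Power = Φ(√(80 × 2/3 × 1/3) × ln 2 − 1.960) = Φ(2.923 − 1.960) = 83.2%. The stated 83% reproduces.

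**Hazards per year.**
- Placebo to AGT: −ln(0.60)/2 = 0.2554
- Hydroxychloroquine to AGT: 0.50 × 0.2554 = 0.1277 (two-year risk 22.5%, as stated)
- Dropout: −ln(0.90)/2 = 0.0527
- Stage 2 to Stage 3: −ln(0.32)/4 = 0.285

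**Time to AGT, dropout or study end.** With h the sum of the AGT and dropout hazards, the mean is (1/h) × [1 − (e^(−2h) − e^(−6h))/(4h)].
- Hydroxychloroquine, h = 0.1804: 2.79 years
- Placebo, h = 0.3081: 2.24 years
- Ratio: 2.79/2.24 = 1.25

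This is time on drug. It is also time under observation if nobody stays after AGT. If half stay until Stage 3, mean observation is 3.06 versus 2.69 years (ratio 1.14). If all stay, it is 3.32 versus 3.13 years (ratio 1.06).

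**Crude incidence, one example.** If observation ends at AGT, incidence is (r/g) × [1 − (e^(−2g) − e^(−6g))/(4g)] with g = h + r. At r = 0.2, hydroxychloroquine (g = 0.3804) gives 40.0% and placebo (g = 0.5081) gives 33.3%, although the true rates are identical.

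**Rejection by the planned test.** The two incidences were put into binomial distributions for 135 and 66, and the probability of a one-sided Fisher p-value of 0.05 or less was summed. HR is 0.50; cells can move by a few tenths of a point with simulation error.

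| Background rate per year | Nobody stays | Half stay | All stay | Equal observation |
|---|---|---|---|---|
| 0.02 | 3.5% | 3.0% | 2.6% | 1.9% |
| 0.05 | 7.6% | 5.6% | 4.1% | 2.8% |
| 0.1 | 12.6% | 8.3% | 5.4% | 3.4% |
| 0.2 | 18.8% | 11.5% | 6.3% | 3.7% |
| 0.5 | 27.7% | 16.2% | 7.2% | 3.6% |
| 1.0 | 29.1% | 16.7% | 6.7% | 3.4% |

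At HR 0.75 with nobody staying, the range is about 2-11%. At HR 1 the arms are observed equally and no bias arises.

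**Reverse direction.** Suppose HR 1.5 and a true rise in an event rate from 0.2 to 0.3 per year (both assumed), with nobody staying. The chance that the planned test detects the rise falls from 36% under equal observation to 12%.

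**Effect of accounting for time.** With nobody staying and HR 0.50, a one-sided conditional test of first events per person-year rejects in 2.9%, 3.5%, 3.7% and 3.9% of trials at rates 0.05, 0.1, 0.2 and 0.5. The crude test rejects in 7.6%, 12.6%, 18.8% and 27.7%.

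**The case against.** A reader might infer that an effective hydroxychloroquine will look falsely toxic because its recipients take it for longer. The documents do not support that as a general statement, for four reasons.

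- **The driver is observation time.** The SAP's window is not limited to time on drug, so unrelated events follow how long participants are watched. Protocol 3.9.2 and 8.1 provide safety assessments after Stage 2. If everyone used that option until Stage 3, the observation ratio would be 1.06 and rejection at most about 7%. The Appendix 2 footnote creates an ambiguity; it does not show that observation stops.
- **The large figures need several conditions together:** the full design effect, poor retention after AGT and common events. At 0.02 per year the test stays below 5% in every scenario.
- **One-sidedness does not cause the bias.** It only places all of the error rate in the direction in which the bias runs when the drug works.
- **Extra events truly caused by longer treatment are not false.**

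Causality assessment also gives some protection. Protocol 8.3 defines toxicity by relatedness and describes these analyses as a way to find patterns and plan later trials. The interruption rules in Protocol 4.5.2 do not use Fisher p-values.

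A further objection concerns the remedy. Replacing crude incidence with events per person-year would mislead for early events. If 20% of each arm had an event confined to the first month, person-years to AGT would turn equal risks into a rate ratio of 2.24/2.79 = 0.80. Protocol 7.2 describes reactions that resolve within one to two weeks on continued therapy, so early events are plausible.

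These points limit the size of the problem and shape the fix. They do not remove the problem: full retention is not secured by the plan, the SAP's organ-class tests are not restricted to related events, and no planned analysis accounts for time.

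**Conclusion.** The concern holds in conditional form. The planned crude comparison is biased toward apparent toxicity if hydroxychloroquine delays AGT and some progressors leave, and in the opposite direction if it hastens AGT. At HR 0.50 the false-signal probability per event category is about 3.5-29%, 3-17% or 2.6-7% with none, half or all of the progressors staying until Stage 3, against about 2-4% under equal observation. The missing multiplicity correction compounds this across system organ classes. The design inputs come from the documents; retention after AGT, background event rates and their constancy are assumptions. Confidence is therefore medium on the size and high on the structure: a head-count denominator, optional follow-up after AGT, and no time-based safety analysis.

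**What to change.** In SAP section 8:

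1. Add a time-to-first-event comparison by system organ class (Kaplan-Meier or Cox) as the basis for between-arm inference. It compares participants still under observation at the same time since randomization, so it handles early events correctly. It does assume that leaving after AGT is unrelated to adverse-event risk, which should be stated.
2. Report person-years under observation and on drug, per arm, in the adverse-event tables. Keep the crude counts and percentages as description.
3. State when event counting ends. Give both an on-treatment version and an all-follow-up version, so that late events are not lost.

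In the Protocol, reconcile sections 3.9.2 and 8.1 with footnote 1 of Appendix 2 on follow-up and adverse-event collection after Stage 2.

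The cost is SAP wording, slightly longer tables and a little more analysis work. No new assessments should be needed, provided that event, dosing and last-contact dates are recorded at the scheduled visits.
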